## **Cardiac Signs and Symptoms**

Based on observations with replicating smallpox vaccines particular attention has been placed on monitoring for cardiac signs and symptoms in all clinical trials using MVA-BN. Despite close cardiac monitoring, no confirmed event indicating a case of myo-/pericarditis has been observed in any completed MVA-BN trial.

## 2.5.2 Safety Profile of MVA-BN-based Recombinant Vaccines in Healthy Compared to Special Populations

BN has evaluated the safety and immunogenicity of MVA-BN-based recombinant vaccines for several indications such as cancer, HIV and measles in more than 700 subjects including healthy and HIV infected populations. In trials with recombinant MVA-BN based vaccines, doses up to  $5 \times 10^8$  TCID50 were administered applying varying schedules of repeated vaccinations, e.g. a 3-dose schedule was used for recombinant HIV vaccines and multiple vaccinations have also been performed in subjects receiving a recombinant therapeutic breast cancer vaccine (MVA-BN-HER2). Results obtained from these Phase I and II trials demonstrate a similar safety profile and vector immunogenicity as compared to MVA-BN alone.

Two of the trials with recombinant vaccines allowed for a direct comparison with MVA-BN as an active control. These trials (HIV-POL-002 and HIV-NEF-004) were performed to evaluate two different recombinant MVA-based HIV vaccine candidates in HIV-infected subjects. In both trials, a total of three vaccinations with either the recombinant HIV vaccine or MVA-BN were performed according to a 0, 8 and 16 week regimen.

[Table 5](#) and [Table 6](#) summarize the safety results of these two trials and demonstrate that there were no significant differences between the recombinant MVA-based vaccine candidates and MVA-BN. For clinical trial HIV-POL-002, singular adverse events are not presented due to the small sample size in this clinical trial (N = 30).

**Table 5      Solicited and Common Unsolicited Adverse Events in Clinical Trial HIV-NEF-004**

	MVA-NEF $1 \times 10^8$ TCID 50 (N = 25)		MVA-NEF $5 \times 10^8$ TCID 50 (N = 26)		MVA-BN $1 \times 10^8$ TCID 50 (N = 26)	
	n	%	n	%	n	%
Solicited AE						
Injection Site Pain	23	92	26	100	26	100
Injection Site Erythema	22	88	24	92	20	77
Injection Site Swelling	22	88	23	89	19	73
Injection Site Induration	19	76	23	89	20	77
Fatigue	16	64	21	81	15	58
Headache	17	68	20	77	14	54
Myalgia	14	56	18	69	12	46
Body temp. increased	3	12	8	31	8	31
Nausea	5	20	4	15	6	23
Chills	2	8	10	39	2	8
Unsolicited AE, irrespective of drug-event relationship / time of onset (N total > 5)						
Nasopharyngitis	6	24	5	19	11	42
Lymphadenopathy	6	24	3	12	6	23
Diarrhea	3	12	5	19	4	15
Headache	4	16	4	15	2	8
Injection site pruritus	1	4	5	19	3	12
Cough	4	16	2	8	2	8
Influenza	3	12	3	12	2	8
Night sweats	2	8	4	15	2	8
Arthralgia	3	12	2	8	2	8
Herpes simplex	3	12	2	8	1	4
Paraesthesia	2	8	3	12	1	4
Unsolicited treatment-related AE during vaccination period (N total > 2)						
Injection site pruritus	1	4	5	19	3	12
Lymphadenopathy	2	8	2	8	2	8

N = Number of subjects in the group; n=number of subjects with AE

Percentages are calculated based on the total number of subjects in the respective group

Source: HIV-NEF-004 Clinical Study Report (August 07, 2008), Table 29.

**Table 6 Unsolicited and Solicited Adverse Events in Clinical Trial HIV-POL-002**

	MVA-BN Polytope <math>1 \times 10^8</math> TCID50 (N = 20)	MVA-BN <math>1 \times 10^8</math> TCID50 (N = 10)
	n (%)	n (%)
Total no. of patients included	20 (100.0)	10 (100.0)
Number of patients with at least one SAE	0	0
Unsolicited AE		
Number of patients with		
- at least one AE	14 (70.0)	7 (70.0)
- at least one related AE	6 (30.0)	4 (40.0)
Unsolicited AEs: Number of AE		
- reported AE	37	19
- average number of AE per subject	1.85	1.90
Solicited local AE		
Number of patients with		
- at least one AE	17 (85.0)	10 (100.0)
Number of solicited local AE	133	69
- average number of AE per subject	6.65	6.90
Solicited general AE		
Number of patients with		
- at least one AE	11 (55.0)	7 (70.0)
Number of solicited general AE	44	28
- average number of AE per subject	2.20	2.80

N = number of patients per treatment group; n = number of patients with AE; % = (n/N)\*100;

Percentages for 'Number of patients with...' were based on the total number of patients included per group.

Solicited local AE: redness, pain, swelling, induration at the injection site; solicited general AEs: body temperature increased, headache, myalgia, rigor/chills, nausea, fatigue

Source: HIV-POL-002 Clinical Study Report (January 12, 2009), Tables 14.3.1.1 and 14.3.5.

### 2.5.3 Immunogenicity Overview of MVA-BN

MVA-BN was tested for safety and immunogenicity among healthy volunteers in 3 Phase I and II dose finding trials ([Vollmar, 2006](#); [Frey, 2007](#); [Von Krempelhuber, 2010](#)). Across these trials a linear dose relationship was observed between the vaccine doses and both vaccinia ELISA and PRNT titers. Maximum ELISA seroconversion rates and peak titers were reached 2 weeks after the second vaccination, with 100 % seroconversion after the second dose for all dose groups receiving at least  $2 \times 10^7$  TCID50 per 0.5 mL dose of MVA-BN. Statistical analysis indicated lower doses to be inferior to the standard dose tested throughout all dose ranging trials, whereas the standard dose achieved ELISA seroconversion rates between 81 and 100 % already after the first dose. For the PRNT, the same trend was observed with about 77 % seroconversion rates 2 weeks after the second MVA-BN administration in all groups receiving the highest dose.

The early onset of seroconversion and the higher titers of total and neutralizing antibodies combined with an excellent safety profile qualified the dose of at least  $5 \times 10^7$  TCID50 as the most suitable human dose. The final optimal (standard) dose and schedule for the general population was decided to be two doses of at least  $5 \times 10^7$  TCID50 MVA-BN (nominal titer of  $1 \times 10^8$  TCID50 per dose) administered SC 4 weeks apart. A trial in elderly, i.e. 56-80 years old vaccination-experienced subjects, indicates that it is sufficient to vaccinate this population only once with MVA-BN.

In the first clinical trial with the MVA-BN-RSV vaccine (RSV-MVA-001 Phase I trial) a low dose with a nominal titer of  $1 \times 10^7$  TCID50 per dose was compared against a dose with a nominal titer of  $1 \times 10^8$  TCID50 per dose (see [Section 2.6](#)).

In this RSV trial (RSV-MVA-002) different doses and schedules will be evaluated: all subjects will receive two vaccinations - either both vaccinations with MVA-BN-RSV vaccine  $1 \times 10^8$  Inf.U per 0.5 mL,  $5 \times 10^8$  Inf.U per 0.5 mL or Placebo or the first vaccination with MVA-BN-RSV vaccine  $1 \times 10^8$  Inf.U or  $5 \times 10^8$  Inf.U per 0.5 mL followed by the second vaccination with Placebo (see [Table 1](#)). Please note that the dose was expressed as TCID50 for the Phase I clinical trial with  $1 \times 10^8$  TCID50 per dose corresponding to  $1 \times 10^8$  Inf.U per dose.

## 2.6 Clinical Trial Data with MVA-BN-RSV Vaccine

Safety, tolerability and immunogenicity of the recombinant MVA-BN-RSV vaccine were evaluated in the randomized, single-blind, placebo-controlled Phase I trial (RSV-MVA-001). In total 63 healthy adult subjects were vaccinated with either placebo, low or normal dose of MVA-BN-RSV vaccine ([Table 7](#)).

**Table 7 Treatment Groups in Phase I Clinical Trial RSV-MVA-001**

Group	N*	Age (years)	Vaccine: nominal titer per dose (TCID 50 )	Volume per dose [mL]	Schedule (vaccination days)	Route
1	18 + 3	18-49	$1 \times 10^7$	0.5	0; 28	IM
2	18 + 3	18-49	$1 \times 10^8$	0.5	0; 28	IM
3	18 + 3	50-65	$1 \times 10^8$	0.5	0; 28	IM
Total	63					

IM = intramuscular; TCID50 = tissue culture infectious dose 50%  
\*18 subjects in each treatment group receiving MVA-BN-RSV vaccine and 3 subjects in each treatment group receiving placebo  
Source: MVA-RSV-001 Clinical Study Report (Ed. 1), Table 1.

63 subjects received two vaccinations 4 weeks apart and completed the active trial phase 4 weeks after the last vaccination. To evaluate long-term safety and immunogenicity of the MVA-BN-RSV vaccine, subjects completed a follow-up (FU) visit 6 months after the second vaccination.

## Safety Data

The trial demonstrated that MVA-BN-RSV was well tolerated in adult and elderly subjects receiving either a low dose ( $1 \times 10^7$  TCID50) or normal dose ( $1 \times 10^8$  TCID50) of the vaccine. No SAEs occurred and no subject discontinued the trial due to an AE. The incidence of solicited local or solicited general AEs was generally low and comparable between analysis groups. A summary of solicited AEs and unsolicited treatment-emergent Adverse Events (TEAEs) is presented in [Table 8](#).

**Table 8 RSV-MVA-001 Trial Summary of Adverse Events per Subject - FAS**

	Analysis group							
	Adult low (N=18)		Adult normal (N=18)		Elderly normal (N=18)		Placebo a (N=9)	
	n (%)	E	n (%)	E	n (%)	E	n (%)	E
Overall (per subject)								
TEAE	14 (77.8)	29	11 (61.1)	26	9 (50.0)	15	5 (55.6)	5
Non-serious TEAE	14 (77.8)	29	11 (61.1)	26	9 (50.0)	15	5 (55.6)	5
SAE b	0	0	0	0	0	0	0	0
Related TEAE c	8 (44.4)	11	7 (38.9)	11	3 (16.7)	5	2 (22.2)	2
TEAE Grade $\geq 3$	0	0	1 (5.6)	2	1 (5.6)	1	0	0
Related TEAE Grade $\geq 3$ c	0	0	0	0	0	0	0	0

E = number of events; FAS = full analysis set; SAE = serious adverse event; TEAE = treatment-emergent adverse event; N = number of subjects per group, n = number of subjects experiencing an AE

a Adult and elderly placebo combined.

b SAEs are included even if they exceed the 28-day follow-up period after each vaccination.

c Unsolicited or general solicited AE the investigator considered to have possible, probable, definite or missing relationship to trial vaccine; although solicited local events are by definition always ADRs they are not included here.

Source: MVA-RSV-001 Clinical Study Report (Ed. 1), Table 15.3.1.1.2.

The most frequently reported unsolicited TEAE was URTI, followed by blood potassium increased. Overall, only few unsolicited TEAEs were considered to be related to trial treatment, all of which were assessed as Grade 1. Furthermore, only 2 subjects were reported as having unsolicited TEAEs assessed as Grade 3 (gastroenteritis and URTI); the majority of subjects had unsolicited TEAEs assessed as Grade 1 and not related to trial treatment.

The most frequent solicited local AEs were injection site pain, injection site erythema, and injection site pruritus; the most frequent solicited general AEs were body temperature increased, fatigue and headache in accordance with the safety profile of the vector backbone MVA-BN (for further details see IB). Solicited local AEs are summarized in [Table 9](#) and related solicited general AEs are summarized in [Table 10](#).

The majority of the solicited local or solicited general AEs were assessed as Grade 1; only few subjects had Grade 2 solicited AEs. Only 1 subject experienced a Grade  $\geq 3$  solicited general AE

of nausea, which was reported as not related to trial treatment. All solicited local and general AEs resolved within 8 days (median  $\leq$ 5 days).

**Table 9     Solicited Local Adverse Events (Overall per Subject) – FAS**

	Number (%) of subjects			
	Adult low (N=18)	Adult normal (N=18)	Elderly normal (N=18)	Placebo a (N=9)
Overall (per subject)				
Injection site erythema	5 (27.8)	4 (22.2)	4 (22.2)	2 (22.2)
Injection site induration	0	1 (5.6)	1 (5.6)	1 (11.1)
Injection site pain	3 (16.7)	9 (50.0)	11 (61.1)	1 (11.1)
Injection site pruritus	2 (11.1)	1 (5.6)	6 (33.3)	0
Injection site swelling	1 (5.6)	1 (5.6)	1 (5.6)	0

FAS = full analysis set  
a Adult and elderly placebo combined.  
 Note: no Grade  $\geq$  3 local Solicited AE was reported  
 Source: MVA-RSV-001 Clinical Study Report (Ed. 1), Table 15.3.1.2.3.

**Table 10    Related Solicited General Adverse Events (Overall per Subject) - FAS**

	Number (%) of subjects			
	Adult low (N=18)	Adult normal (N=18)	Elderly normal (N=18)	Placebo a (N=9)
Body temperature increased	4 (22.2)	3 (16.7)	0	0
Chills	0	0	0	0
Fatigue	3 (16.7)	2 (11.1)	1 (5.6)	1 (11.1)
Headache	1 (5.6)	2 (11.1)	2 (11.1)	0
Myalgia	1 (5.6)	0	2 (11.1)	0
Nausea	1 (5.6)	1 (5.6)	0	0

FAS = full analysis set  
a Adult and elderly placebo combined.  
 Note: Relationship summarized as all symptoms determined by the investigator with reasonable possibility that the vaccine contributed to them (relationship to vaccine documented as 'possible', 'probable', 'definite' or missing).  
 Source: MVA-RSV-001 Clinical Study Report (Ed. 1), Table 15.3.1.3.5.

## Immunogenicity Data

The primary objective of this Phase I trial was the collection of safety data. The trial had a small sample size and was not powered for testing RSV-specific immunogenicity thus the immunogenicity results are descriptive and only of exploratory nature.

### Antibody Analyses:

RSV-specific GMTs increased after vaccination in all groups receiving MVA-BN-RSV compared with placebo in the ELISA and PRNT strain A analyses. An at least 2-fold increase was shown for the adult standard dose group for both assays and for the elderly standard dose group for the RSV-specific ELISA. The neutralizing antibody titer measured by PRNT in the elderly standard dose group was lower than in the adult standard dose group; serum RSV-specific baseline and individual peak geometric mean titers by ELISA, PRNT (strain A) and PRNT (strain B) are summarized in [Table 11](#).

**Table 11 Serum RSV-Specific Baseline and Individual Peak Geometric Mean Titers – FAS and PPS**

	Analysis group							
	Adult low (N=18 b )		Adult standard (N=18)		Elderly standard (N=18)		Placebo a (N=9)	
Week (Visit)	GMT	95% CI	GMT	95% CI	GMT	95% CI	GMT	95% CI
Serum RSV-specific IgG ELISA GMT								
Week 0 (V1)	1146	915, 1437	1121	830, 1512	913	726, 1149	1005	710, 1422
Individual Peak GMT	1807	1435, 2276	2238	1622, 3089	2286	1725, 3030	1289	913, 1820
Serum RSV-specific PRNT (strain A) GMT								
Week 0 (V1)	546	380, 783	652	474, 897	625	456, 857	524	374, 734
Individual Peak GMT	926	676, 1268	1394	1087, 1788	944	677, 1315	782	560, 1093
Serum RSV-specific PRNT (strain B) GMT								
Week 0 (V1)	256	173, 379	327	190, 561	242	154, 380	231	116, 456
Individual Peak GMT	379	245, 587	512	322, 814	374	231, 604	347	189, 636
CI = confidence interval; ELISA = enzyme-linked immunosorbent assay; FAS = full analysis set; GMT = geometric mean titers; IgG = immunoglobulin G; PPS = per protocol set; RSV = respiratory syncytial virus								
a Adult and elderly placebo combined.								
b Only 17 of 18 subjects had available data in this group at Week 8 (V7).								
Source: MVA-RSV-001 Clinical Study Report (Ed. 1), Tables 15.2.2.5, 15.2.4.5 and 15.2.5.5.								

The cellular immune response was assessed using an IFN- $\gamma$ /IL-4 ELISPOT assay using three different RSV peptide pools (F, G and N) as well as RSV for stimulation. IFN- $\gamma$  secreting T cells specific for the F, G and N protein increased in all active treatment groups, with no substantial differences between vaccine dose and age whereas numbers of IL-4 producing T cells were low or below the detection limit. No dose dependency was seen in terms of Geometric Mean Spot Forming Units (GMSFUs). The T cell response boosted by the normal dose in the adult and elderly group was comparable. The responder rate based on IFN- $\gamma$  producing PBMCs was highest in the elderly standard dose group, ranging from 66.7% (12/18) to 94.4% (17/18) of subjects for all stimulating agents. Responder rates based on IFN- $\gamma$  and IL-4 producing PBMCs are summarized in [Table 12](#).

These results showed that the MVA-BN-RSV candidate leads to an increase in the number of IFN- $\gamma$  producing T cells without inducing IL-4 secreting T cells, thus limiting the risk for emergence of enhanced disease by biasing the immune response strongly towards a Th1 type response.

**Table 12 PBMC ELISPOT: IFN- $\gamma$ /IL-4 Responder Rates – FAS and PPS**

	Analysis group							
	Adult low a (N=18)		Adult standard (N=18)		Elderly standard (N=18)		Placebo b (N=9)	
	IFN- $\gamma$	IL-4	IFN- $\gamma$	IL-4	IFN- $\gamma$	IL-4	IFN- $\gamma$	IL-4
	ER (%)	ER (%)	ER (%)	ER (%)	ER (%)	ER (%)	ER (%)	ER (%)
	95% CI	95% CI	95% CI	95% CI	95% CI	95% CI	95% CI	95% CI
Pool F	7 (43.8) 19.8, 70.1	1 (6.3) 0.2, 30.2	7 (38.9) 17.3, 64.3	1 (5.6) 0.1, 27.3	14 (77.8) 52.4, 93.6	1 (5.6) 0.1, 27.3	0 0.0, 33.6	0 0.0, 33.6
Pool G	7 (43.8) 19.8, 70.1	2 (12.5) 1.6, 38.3	16 (88.9) 65.3, 98.6	1 (5.6) 0.1, 27.3	17 (94.4) 72.7, 99.9	1 (5.6) 0.1, 27.3	0 0.0, 33.6	0 0.0, 33.6
Pool N	7 (43.8) 19.8, 70.1	1 (6.3) 0.2, 30.2	10 (55.6) 30.8, 78.5	0 0.0, 18.5	12 (66.7) 41.0, 86.7	0 0.0, 18.5	1 (11.1) 0.3, 48.2	0 0.0, 33.6
RSV	8 (50.0) 24.7, 75.3	2 (12.5) 1.6, 38.3	10 (55.6) 30.8, 78.5	5 (27.8) 9.7, 53.5	15 (83.3) 58.6, 96.4	1 (5.6) 0.1, 27.3	0 0.0, 33.6	0 0.0, 33.6

CI = confidence interval; ELISPOT = enzyme-linked immunospot technique; FAS = full analysis set;  
IFN- $\gamma$  = interferon gamma; IL-4 = interleukin 4; PPS = per protocol set; ER (%) = Number of subjects with positive ELISPOT responder status (percentage of subjects with positive responder status based on number of subjects with available data); RSV = respiratory syncytial virus

a Only 16 of 18 subjects had available data in this group.

b Adult and elderly placebo combined.

Note: At least 2 post Week /V1 responses are required for the subject to be defined as a responder.

Source: MVA-RSV-001 Clinical Study Report (Ed. 1), Table 15.2.16.1 and Table 15.2.16.3.

## 2.7 Rationale

As outlined in [Section 2](#), RSV is an important cause of serious respiratory disease in all age groups. The recently completed Phase I clinical trial RSV-MVA-001 generated first safety and immunogenicity data of the recombinant MVA-BN-RSV vaccine in healthy adult subjects 18-65 years of age. This trial confirmed that the vaccine is safe and well tolerated and was able to increase humoral and cellular immune responses in the population tested.

The main trial is designed to evaluate different doses of the MVA-BN-RSV vaccine in a target population of adult/elderly subjects in terms of immunogenicity and safety.

As RSV is a seasonal disease with peak occurrence in the winter months in the northern hemisphere vaccination for protection against moderate to severe respiratory tract infections caused by RSV would be scheduled shortly before the start of the RSV season. Depending on the durability of the immune responses elicited by a vaccination a yearly booster before the next RSV season might be necessary. Hence a substudy applying a booster vaccination in a subgroup of the main trial will evaluate the durability of the immune response and the ability to booster with the MVA-BN-RSV vaccine.

The objective of the booster substudy is to demonstrate that the immune response of subjects previously vaccinated with MVA-BN-RSV vaccine can be boosted one year later with a single MVA-BN-RSV vaccination. Assessment of individual antibody titers within short time intervals following the booster vaccination and up to 12 months after the vaccination will provide information on how fast and effective measurable antibody titers can be regained. The booster substudy will also evaluate the durability of immune responses 12 months following the primary vaccination (baseline measurement prior to administration of the booster dose) and 12 months following the booster vaccination.

The selection of the treatment groups to be included in the booster substudy is based on the results of the main trial. Selecting subjects of two groups for a booster vaccination will add a one year time point for the two most promising dose regimen treatment groups and will allow to identify further potential differences in durability or boostability of immune responses in the chosen dose regimens. Half of the subjects enrolled for the main part of the trial in the two chosen treatment groups will receive the same vaccine dose (either  $1 \times 10^8$  or  $5 \times 10^8$  Inf.U) as in the main part. The two groups to continue into the booster substudy will be selected by the sponsor. The subjects from the remaining groups will be excluded from the booster substudy as the further development of their dose regimen is unlikely at the current time.

## 2.8 Trial Population

Any  $\geq 55$  year old women and men of any ethnicity who meet all of the inclusion and none of the exclusion criteria are eligible for participation in this trial.

Groups will be stratified by age: 55 to  $< 70$ ,  $\geq 70$  years in the main part of the trial. For the booster substudy 43 evaluable subjects will be chosen randomly from each of the two selected treatment groups. No further age stratification will be done in the booster substudy.

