### 5.1 Recruitment Procedure

Subjects will be recruited actively. Recruitment strategies, including IRB approved advertisements, will be evaluated by the Sponsor.

80 subjects will be recruited in each group (400 in total) according to the treatment group schedule, [Table 13](#).

After signing the ICF and HIPAA, subjects undergo screening procedures to check eligibility according to the inclusion/exclusion criteria. In the event of a screening failure due to mild or limited acute illness or abnormal laboratory values, the subject may be re-screened after resolution of the event. Re-screening may require only an additional blood draw or a complete re-screening evaluation, depending on the circumstances of and the time interval from the initial screening failure (see also [Section 4.2.1](#)).

From each of the two treatment groups selected for the booster substudy, 43 subjects will be randomly recruited to receive a booster vaccination approximately one year after their first vaccination with the same dose they had received during the main trial. Out of these 86 subjects, in total approximately 26 subjects will be recruited from the PBMC subgroup resulting in approximately 13 subjects for each of the two selected treatment groups.

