### 9.1 Randomization Procedure and Blinding

The main part of the trial is randomized using an automated randomization system, integrated in the eCRF: Details on the randomization will be outlined in a separate randomization specification.

Assignment to the groups is done in a randomized manner. The main trial is single-blinded, i.e. subjects will be blinded to the group assignment.

In total 86 subjects from two selected treatment groups will be chosen randomly for the booster substudy outlined in a separate randomization specification.

For details on staggering and randomization refer to trial protocol synopsis (see [Sections 1.5](#) and [4.1](#)).

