## **2.2 Design Techniques to Avoid Bias**

Eligible subjects who have consented to participate in the booster sub-study will be enrolled until a total of 86 is reached. PBMC sites will begin recruitment 1-2 weeks prior to the remaining sites to ensure 13 PBMC subjects per treatment group. Once 46 subjects are enrolled into one treatment group, enrolment for that group will stop to assure an approximately equal number of enrolled subjects in both treatment groups.

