### **2.2.1 Methods of Assigning Subjects to Treatment Groups**

Subjects in this booster sub-study will not be randomized. They will get the same dose received during the main study.

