## 4 Statistical Methods

### 4.1 Planned Sample Size

From two treatment groups selected based on immunogenicity/safety parameters following primary vaccination, approximately 43 subjects will be recruited into the booster sub-study (86 subjects in total). Out of these 86 subjects, approximately 26 subjects (13 subjects for each dose group) will be recruited from the PBMC subgroup.

Based on the variability observed in the  $\log_{10}$  titers for PRNT (A strain) 2 weeks after the second vaccination in the main study, the standard deviation (SD) is estimated to be 0.335 for the  $\log_{10}$  titers 2 weeks after the booster vaccination. A total of 40 evaluable subjects per group will provide 80% power to detect a difference of 0.213 ( $\log_{10}$ -scale) at a significance level of 5% (two-sided), which corresponds to a ratio of 1.63 in GMTs. Considering a drop-out rate of 5%, 43 subjects per group will be enrolled to receive a booster vaccination.

The sample size for the main study has been initially estimated based on the need to detect a significant difference between the two doses to select the optimal dose for further development. However, only a descriptive comparison is planned between the two dose groups in the sub-study.

The primary objective of the booster sub-study is to demonstrate that the immune response of subjects previously vaccinated with MVA-BN-RSV vaccine can be boosted one year later with a single MVA-BN-RSV vaccination. When the sample size is 40, a paired t-test with a 0.025 one-sided significance level will have >80% power to reject the null hypothesis that the difference in immune response ( $\log_{10}$  titers) after the initial vaccination and that after the booster vaccination is 0.08 or farther from zero when the expected difference is 0, assuming that the standard deviation of the differences is 0.168 ( $\log_{10}$ -scale). This comparison is also considered descriptive.

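### The protocol selects booster subjects at random, 43 per group; the booster SAP enrols consenters with a stop at 46 per group and does not declare the departure

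*Protocol*

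**What the plan says.** **Protocol, Edition 4.0.** Random selection appears three times:

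- Section 2.8: "43 evaluable subjects will be chosen randomly from each of the two selected treatment groups".
- Section 5.1: "43 subjects will be randomly recruited to receive a booster vaccination approximately one year after their first vaccination".
- Section 9.1: "In total 86 subjects from two selected treatment groups will be chosen randomly for the booster substudy outlined in a separate randomization specification".

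Section 4.1 (Booster Substudy) makes 43 per group a maximum, chosen to yield 40 evaluable. Section 9.2 gives the reasoning: 40 evaluable per group, inflated for 5% drop-out. Section 5.1 also sets a quota of about 13 PBMC-subgroup subjects per group.

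**Booster SAP.** Section 1 states that it is based on Edition 4.0, so the difference is not due to superseded text. Section 2.2 gives the enrolment rule: "Eligible subjects who have consented to participate in the booster sub-study will be enrolled until a total of 86 is reached". PBMC sites open 1-2 weeks before the others, and the only per-group limit is this: "Once 46 subjects are enrolled into one treatment group, enrolment for that group will stop". No draw is described. Section 4.1 repeats the protocol's figures, including 43 enrolled per group and the statement that "A total of 40 evaluable subjects per group will provide 80% power". Section 4.6, which lists alterations from the protocol, names only the memory B cell analyses.

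Section 2.2.1 adds that "Subjects in this booster sub-study will not be randomized", but its heading concerns assignment to treatment. It does not settle how subjects are selected, and this point does not rely on it.

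**The concern.** The two documents describe different sampling procedures for the same substudy. A site or a reader of the CSR cannot tell which one governed.

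A random draw within each group would make those invited a fair sample of Groups 1 and 3, whatever happens afterwards at consent. Under the SAP rule, the order in which people come forward, and which sites open first, help decide who is in. The main-study SAP (section 1.1) says three sites recruited all PBMC subjects, and the protocol synopsis allows up to 16 sites, so a head start for the PBMC sites could change the site mix. Protocol 2.8 drops age stratification for the booster substudy, so the draw is the only step described there for keeping the boosted subset representative of its group.

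At stake is how far booster results can stand for Groups 1 and 3, and how comparable the boosted subsets are when booster SAP 4.5.7 reports Group 3/Group 1 ratios of GMTs and fold increases. The cap of 46 also exceeds the protocol's maximum of 43 and lets the other group close at 40 enrolled, which leaves no allowance for drop-out.

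**Working it through.** **1. The plan's own figure.** Inputs from Protocol 9.2 and booster SAP 4.1: SD 0.335 (log10), difference 0.213, two-sided 5%, 40 evaluable per group, 5% drop-out.

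- Noncentrality = 0.213 / (0.335 × √(1/40 + 1/40)) = 2.84. The two-sample t-test has power 0.802.
- 10^0.213 = 1.63, the stated GMT ratio.
- 40 / 0.95 = 42.1, rounded up to 43.

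The stated 80%, 1.63 and 43 are all reproduced.

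**2. What the cap permits.** With a total of 86 and one group at 46, the other has 86 − 46 = 40 enrolled. Expected evaluable at 5% drop-out:

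| Split enrolled | Larger group | Smaller group |
|---|---|---|
| 43:43 | 43 × 0.95 = 40.85 | 40.85 |
| 46:40 | 46 × 0.95 = 43.7 | 40 × 0.95 = 38.0 |

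The smaller group is 2 below the stated 40 in expectation.

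**3. Chance of reaching 40 evaluable.** Assume each subject drops out independently with probability 0.05. This is my assumption; the documents give only the rate.

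- 40 enrolled: 0.95^40 = 0.129.
- 43 enrolled: 0.833.
- 46 enrolled: 0.992.
- Both groups reach 40: 0.833² ≈ 0.695 at 43:43, and 0.992 × 0.129 ≈ 0.128 at 46:40.

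**4. Power at the cap.**

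- Between groups, 43.7 against 38: noncentrality = 0.213 / (0.335 × √(1/43.7 + 1/38)) = 2.87, power 0.808. At 40.85 against 40.85 it is 0.810.
- Paired comparison of booster SAP 4.1 (margin 0.08, SD of differences 0.168, one-sided 0.025, read as a single one-sided test): noncentrality = 0.08 / (0.168/√n). Power is 0.836 at n = 40 and 0.816 at n = 38.

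Both stay above 80%.

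**5. Selection.** No arithmetic applies. Neither document gives anything from which the bias of first-come enrolment could be sized.

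**The case against.** **Self-selection exists under either rule.** A reader might infer that the discrepancy is what makes the sample self-selected. The documents do not support that. Every booster subject must sign a new consent form (Protocol 11), and refusal of the booster is an exclusion criterion (protocol synopsis). Subjects may be told their dosage group after FU2 (Protocol 4.2.1.3). Someone who knows the dose and remembers the reactions can decline whether or not a draw took place, and refusal could differ by dose in both cases. This objection stands. What remains is narrower: the SAP removes the draw and puts order of arrival in its place.

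**The boosted fraction is not a measure of bias.** A reader might take 86 of 158 vaccinated subjects in Groups 1 and 3 (78 + 80; 54%) as the size of the problem. Protocol 2.7 already plans to boost half of each selected group, so a random draw would leave a similar fraction.

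**The PBMC head start serves a protocol quota.** This is true, so selection was never a simple random sample of each group. A draw made separately within the PBMC subgroup would meet the quota as well.

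**A draw may be described elsewhere.** Protocol 9.1 points to a separate randomization specification that is not among the documents. A random order of invitation cannot be excluded, but booster SAP 2.2 leaves no evident place for one.

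**Representativeness can partly be checked already.** Booster SAP 4.5.7 tabulates the boosted subjects' main-trial PRNT A titers, and the main-study tables give age and titers for the full groups. That sets a subset against a whole that contains it, and it leaves out the boosted subjects' main-trial solicited AEs. No listed table compares boosted with non-boosted subjects.

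**Conclusion.** There is an undeclared inconsistency between the current protocol and the booster SAP that claims to follow it. They differ on how subjects are selected (random draw against enrolment of consenters as they come) and on the per-group limit (43 against 46). The SAP also disagrees with itself, since its section 4.1 still states 43 per group.

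The numerical effect is small. In the worst split the rule permits, the smaller group has about 38 expected evaluable against 40, assuming the planned 5% drop-out and enrolment ending exactly at the cap. Even 43:43 does not guarantee 40 in both groups: under independent drop-out there is about a 31% chance (1 − 0.695) that at least one falls short, against about 87% (1 − 0.128) at 46:40. A reader might infer a loss of power from this; there is no material one, and both comparisons are declared descriptive.

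The effect of losing the draw is unknown in size and direction. The paired, within-subject comparison is less exposed to it than the Group 3/Group 1 ratios. The point is worth correcting because the protocol promises random selection and the report would otherwise carry that promise without a basis in the SAP.

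**What to change.** **If enrolment is not complete:** invite from a randomly ordered list within each group, drawn separately within the PBMC subgroup so that its quota of about 13 per group is met. Cap each group at 43. Issue invitations early enough, or in large enough batches, to keep BV1 at about 11-13 months after the first vaccination (Protocol 1.7, footnote 11). Amend booster SAP 2.2 to match. The cost is some enrolment flexibility.

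**If enrolment has already followed SAP 2.2:**

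- Leave the protocol wording as it is. Removing the word for random after the fact would rewrite the plan.
- List the departure in SAP 4.6 and report it in the CSR.
- State that the smaller group may have about 38 evaluable subjects, and correct the 43 per group in SAP 4.1.
- Add one table comparing boosted with non-boosted subjects, separately for Groups 1 and 3, on age, V1 and V2 PRNT A titers and main-trial solicited AEs.

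The table uses data already collected, so this route costs a few lines of SAP and CSR text and one output.
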